### **Incomplete/missing data:**

- Imputation rules for missing prior/concomitant medications, non-study vaccinations and procedures are provided in [Appendix C](#)
- Imputation rules for missing AE dates are provided in [Appendix D](#)
- If antibody values reported as below the LLOQ (e.g., <0.1), the numeric values will be imputed by  $0.5 \times \text{LLOQ}$  in the summary. If antibody values reported as greater than the ULOQ (e.g., >3000), the numeric values will be imputed by ULOQ in the summary if actual values are not available
- Other incomplete/missing data will not be imputed, unless specified otherwise

The following treatment groups will be used for summary purposes:

#### Part A

- mRNA-1283 vaccine **CCI**
- mRNA-1283 vaccine **CCI**
- mRNA-1283 vaccine **CCI**
- mRNA-1283.211 vaccine **CCI**
- mRNA-1283.211 vaccine **CCI**
- mRNA-1273 vaccine **CCI**

#### Part B

- mRNA-1283.529 vaccine **CCI**
- mRNA-1283.529 vaccine **CCI**

All analyses will be conducted using SAS Version 9.4 or higher.

## **6.2. Background Characteristics**

The following summary analyses will be similar for Part A and Part B.

### **6.2.1. Subject Disposition**

The number and percentage of subjects in the following categories will be summarized by treatment group as defined in [Section 6.1](#) based on the Randomized/Enrolled Set:

- Randomized Set (Part A only)

- Enrolled Set (Part B only)
- FAS
- PPIS
- PPIS-Neg
- Safety Set
- Solicited Safety Set

Percentages will be based on the number of subjects in the treatment group within the Randomized/Enrolled Set (as randomized/enrolled). For Solicited Safety Set, the percentage will be based on the number of subjects in the treatment group within the Safety Set (as treated).

Summary of reasons for subjects excluded from the PPIS, PPIS-Neg analysis sets will also be provided.

The number of subjects in the following categories will be summarized based on subjects screened:

- Number of subjects screened
- Number and percentage of screen failure subjects and the reason for screen failure

The percentage of subjects who screen failed will be based on the number of subjects screened. The reason for screen failure will be based on the number of subjects who screen failed.

The number and percentage of subjects in each of the following disposition categories will be summarized by treatment group based on the Randomized/Enrolled Set:

- Received IP
- Completed study
- Prematurely discontinued the study and the reason for discontinuation

This study treatment consists of a single booster, thus discontinuation from study treatment is not applicable to this study. A subject is considered to have completed the study if he or she has completed the study including the last scheduled procedure as shown in the SoE (Table 8 in the Protocol).

A subject disposition listing will be provided, including the information about ICF completion, IPs received, Study completion and EoS reasons if discontinuation from the study. A separate listing will be provided for screen failure subjects with reasons for screen failure.

### **6.2.2. Demographics**

Descriptive statistics for demographics and baseline characteristics will be calculated for the following continuous variables: age (years), weight (kg), height (cm), and body mass index (BMI) (kg/m^2). Number and percentage of subjects will be provided for categorical variables such as age group (18-55,  $\geq$ 56 years of age), gender, race, ethnicity, pre-booster SARS-CoV-2 infection status, and duration in months from completion of primary series to booster dose. The summaries will be presented by treatment group as defined in [Section 6.1](#) based on the randomization/enrollment set, Safety Set, PPIS and PPIS-Neg.

In addition, randomized/enrolled subjects with any inclusion and exclusion criteria violations will also be provided in a listing.

### **6.2.3. Medical History**

Medical history data will be coded by system organ class (SOC) and preferred term (PT) using the latest version of Medical Dictionary for Regulatory Activities (MedDRA) when the analyses are performed.

The number and percentage of participants with any medical history will be summarized by SOC and PT based on the Safety Set. Angioedema, anaphylaxis and hypersensitivity will be summarized separately by preferred term. A participant will be counted only once for multiple events within each SOC and PT. SOC will be displayed in internationally agreed order. PT will be displayed in descending order of frequency of mRNA-1273 **CCI** group for Part A and mRNA-1283.529 10 ug for Part B, and then alphabetically within SOC.

Medical history data will be presented in a listing.

### **6.2.4. Concomitant Medications**

Concomitant medications and non-study vaccination will be coded using the World Health Organization (WHO) drug dictionary (WHODD). The summary of concomitant medications will be based on the Safety Set. Categorization of concomitant, and post medications is summarized in [Appendix C Table 4](#).

The number and percentage of subjects using concomitant medications and non-study vaccination will be summarized by follow-up period and treatment group as defined in [Section 6.1](#). Antipyretic, or analgesic medication (pain or fever-), along with seasonal influenza and non-study vaccines will be summarized separately. The tables will be sorted by SOC in internationally agreed order and PT in descending frequency based on mRNA-1273 group for Part A, mRNA-1283.529 **CCI** group for Part B.

Prior, concomitant and post medications and non-study vaccination will be presented in a listing. Concomitant Procedures will be presented in a listing.

#### **6.2.5. Study Exposure**

Study vaccine administration data will be presented in a listing.

Study duration will be summarized since randomization/enrollment, and- since the study injection based on Safety Set.

#### **6.2.6. Major Protocol Deviations**

Major protocol deviations are a subset of protocol deviations that may significantly impact the completeness, accuracy, or reliability of the study data or that may significantly affect a subject's rights, safety, or well-being. Major protocol deviations rules will be developed and finalized before database lock.

The number and percentage of the subjects with each major protocol deviation type will be provided by treatment group as defined in [Section 6.1](#) based on the Randomized/Enrolled Set. Major protocol deviations will be presented in a listing.

#### **6.2.7. COVID-19 Impact**

A listing will be provided for COVID-19 impact on missed or out of window visits or assessments for subjects in Safety Set.

### **6.3. Safety Analysis**

Part A and B:

Safety and reactogenicity will be assessed by clinical review of all relevant parameters including solicited ARs (local and systemic ARs), unsolicited AEs, treatment-related AEs, severe AEs, SAEs, MAAEs, AESIs and AEs leading to withdrawal from study participation (Table 5 in the protocol). The Toxicity Grading Scale for Healthy Adult and

Adolescent Volunteers Enrolled in Preventative Vaccine Clinical Trials ([DHHS 2007](#)) is used in this study for solicited ARs.

All safety analyses will be based on the Safety Set, except summaries of solicited ARs, which will be based on the Solicited Safety Set. All safety analyses will be provided by treatment group. Participants will be included in the treatment group corresponding to the IP that they actually received.

### **6.3.1. Adverse Events**

A treatment-emergent AE (TEAE) is defined as any event not present before exposure to study vaccine or any event already present that worsens after exposure to study vaccine. [Note: worsening of a pre-existing condition after vaccination will be reported as a new AE.]

Adverse events will also be evaluated by the investigator for the coexistence of MAAE which is defined as an AE that leads to an unscheduled visit to a healthcare practitioner. All confirmed COVID-19 cases will be recorded as MAAEs.

AEs of special interest (AESI) are defined in Appendix 4 of the protocol.

Unsolicited AEs will be coded by PT and SOC using the latest MedDRA available at the analyses and summarized by treatment group and follow-up period (defined in [Section 6.1](#)).

All summary tables (except for the overall summary of AEs) for unsolicited AEs will be presented by SOC and PT for TEAEs with counts of subjects included. SOC will be displayed in internationally agreed order. PT will be displayed in descending order of frequency of mRNA-1273 **CCI** and then alphabetically within SOC. When summarizing the number and percentage of subjects with an event, subjects with multiple occurrences of the same AE or a continuing AE will be counted once. Subjects will be presented according to the highest severity in the summaries by severity, if subjects reported multiple events under the same PT.

Percentages will be based upon the number of subjects in the Safety Set within each treatment group.

#### **6.3.1.1. Incidence of Adverse Events**

An overall summary of unsolicited TEAEs including the number and percentage of subjects who experience the following will be presented:

- Any unsolicited TEAEs
- Any serious TEAEs
- Any fatal TEAEs
- Any unsolicited MAAEs
- Any unsolicited TEAEs leading to discontinuation from participation in the study
- Any unsolicited severe TEAEs
- Any unsolicited AESIs

The same table will also include number and percentage of subjects with unsolicited TEAEs that are treatment-related per PI's assessment in each of the above categories.

The above overall summaries will be done for unsolicited non-serious TEAEs with applicable TEAE categories.

In addition, Unsolicited AEs, unsolicited TEAEs leading to discontinuation from the study, serious AEs, unsolicited MAAEs, and AESIs, will be listed. AESI other than myocarditis and pericarditis; AESI of myocarditis and pericarditis, will be provided separately.

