#### **Events NOT Meeting the Adverse Event Definition**

- Procedures planned before study entry (eg, hospitalization for preplanned surgical procedure).
- Medical or surgical procedure (eg, endoscopy, appendectomy): the condition that leads to the procedure should be the AE.
- Situations in which an untoward medical occurrence did not occur (social and/or convenience admission to a hospital).

An AR is any AE for which there is a reasonable possibility that the vaccine caused the AE ([Section 7.4.3](#)). For the purposes of investigational new drug safety reporting, “reasonable possibility” means that there is evidence to suggest a causal relationship between the vaccine and the AE.

An unsolicited AE is any AE reported by the participant that is not specified as a solicited AR in the protocol or is specified as a solicited AR but starts outside the protocol-defined period for reporting solicited ARs (ie, 7 days after vaccination).

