**Table 5: Solicited Adverse Reactions and Grades**

Reaction	Grade 0	Grade 1	Grade 2	Grade 3	Grade 4
Injection site pain	None	Does not interfere with activity	Repeated use of over-the-counter pain reliever > 24 hours or interferes with activity	Any use of prescription pain reliever or prevents daily activity	Requires emergency room visit or hospitalization
Injection site erythema (redness)	< 25 mm/ < 2.5 cm	25 - 50 mm/ 2.5 - 5 cm	51 - 100 mm/ 5.1 - 10 cm	> 100 mm/ > 10 cm	Necrosis or exfoliative dermatitis
Injection site swelling/induration (hardness)	< 25 mm/ < 2.5 cm	25 - 50 mm/ 2.5 - 5 cm	51 - 100 mm/ 5.1 - 10 cm	> 100 mm/ > 10 cm	Necrosis
Axillary (underarm) swelling or tenderness ipsilateral to the side of injection	None	No interference with activity	Repeated use of over-the-counter (non-narcotic) pain reliever > 24 hours or some interference with activity	Any use of prescription (narcotic) pain reliever or prevents daily activity	Emergency room visit or hospitalization
Headache	None	No interference with activity	Repeated use of over-the-counter pain reliever > 24 hours or some interference with activity	Significant; any use of prescription pain reliever or prevents daily activity	Requires emergency room visit or hospitalization

Reaction	Grade 0	Grade 1	Grade 2	Grade 3	Grade 4
Fatigue	None	No interference with activity	Some interference with activity	Significant; prevents daily activity	Requires emergency room visit or hospitalization
Myalgia (muscle aches all over body)	None	No interference with activity	Some interference with activity	Significant; prevents daily activity	Requires emergency room visit or hospitalization
Arthralgia (joint aches in several joints)	None	No interference with activity	Some interference with activity	Significant; prevents daily activity	Requires emergency room visit or hospitalization
Nausea/vomiting	None	No interference with activity or 1-2 episodes/24 hours	Some interference with activity or > 2 episodes/24 hours	Prevents daily activity, requires outpatient intravenous hydration	Requires emergency room visit or hospitalization for hypotensive shock
Chills	None	No interference with activity	Some interference with activity not requiring medical intervention	Prevents daily activity and requires medical intervention	Requires emergency room visit or hospitalization

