Fever (oral)	< 38.0°C < 100.4°F	38.0 – 38.4°C 100.4 – 101.1°F	38.5 – 38.9°C 101.2 – 102.0°F	39.0 – 40.0°C 102.1 – 104.0°F	> 40.0°C > 104.0°F

Note: Events listed above but starting > 7 days after study injection will be recorded on the AE CRF. Causality for each event will be determined per assessment by the investigator.

Any solicited AR that meets any of the following criteria must be entered into the participant's source document and must also be recorded by the study site staff on the solicited AR page of the participant's eCRF:

- Solicited local or systemic AR that results in a visit to a healthcare practitioner (HCP), to be recorded as an MAAE ([Section 7.4.4](#))
- Solicited local or systemic AR leading to the participant withdrawing from the study or the participant being withdrawn from the study by the investigator (AE leading to withdrawal)

- Solicited local or systemic AR lasting beyond 7 days post-injection
- Solicited local or systemic AR that otherwise meets the definition of an SAE

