**Table 7: Analysis Strategy for Safety Parameters**

Safety Endpoint	Number and Percentage of Participants, Number of Events	95% CI for Each Treatment Group
Any Solicited AR (overall and by local, systemic)	X	X
Any Unsolicited AE	X	—
Any SAE	X	—
Any Unsolicited MAAE	X	—
Any Unsolicited AESI	X	—
Any Unsolicited Treatment-Related AE	X	—
Any Treatment-Related SAE	X	—
Any Unsolicited AE Leading to Withdrawal from Study Participation	X	—
Any Severe Unsolicited AE	X	—
Any Treatment-Related Severe Unsolicited AE	X	—

Abbreviations: AE = adverse event; AESI = adverse event of special interest; AR = adverse reaction; CI = confidence interval; MAAE = medically attended adverse event; SAE = serious adverse event.

Notes: 95% CI using the Clopper-Pearson method, X = results will be provided.

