## **3. Study Endpoints**

### **3.1. Part A Endpoints**

#### **3.1.1. Primary Endpoints**

The primary objective will be evaluated by the following endpoints:

- Frequency and grade of each solicited local and systemic reactogenicity adverse reaction (AR) during a 7-day follow-up period after vaccination
- Frequency and severity of any unsolicited adverse events (AEs) during the 28-day follow-up period after vaccination
- Frequency of any serious AEs (SAEs), medically attended AEs (MAAEs), AEs leading to withdrawal from study participation, and AEs of special interest (AESIs) from Day 1 to end of study (EoS)
- Immune response of the mRNA-1283 and mRNA-1283.211- vaccines against the ancestral SARS-CoV-2 and SARS-CoV-2 variants, including B.1.351 and B.1.1.529, at Day 29 by geometric mean titer (GMT), geometric mean fold rise (GMFR), and seroresponse rate (SRR)
- To compare descriptively the immune response elicited by the mRNA-1283 and mRNA-1283.211 - vaccines with that elicited by the mRNA-1273 vaccine when administered as a booster, at Day 29 by GMT, GMFR, and SRR

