## **3.2. Part B Endpoints**

### **3.2.1. Primary Endpoints**

The primary objective will be evaluated by the following endpoints:

- Frequency and grade of each solicited local and systemic reactogenicity AR during a 7-day follow-up period after vaccination
- Frequency and severity of any unsolicited AEs during the 28-day follow-up period after vaccination
- Frequency of any SAEs, MAAEs, AEs leading to withdrawal from study participation, and AESIs from Day 1 to EoS
- Immune response of the mRNA-1283.529 vaccine by dose level against SARS-CoV-2 Omicron variant (B1.1.529) at Day 29 by GMT, GMFR, and SRR

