### **6.3.1.2. TEAEs by System Organ Class and Preferred Term**

The following summary tables of TEAEs will be provided by SOC (in internationally agreed order) and PT using frequency counts and percentages (i.e., number and percentage of subjects with an event):

- All unsolicited TEAEs
- All unsolicited TEAEs that are treatment-related
- All serious TEAEs
- All serious TEAEs that are treatment-related
- All unsolicited TEAEs leading to discontinuation from participation in the study
- All unsolicited Severe TEAEs
- All unsolicited Severe TEAEs that are treatment-related
- All unsolicited TEAEs that are medically-attended
- All unsolicited medically-attended TEAEs that are treatment-related

- All AESIs of myocarditis and/or pericarditis
- All AESIs other than myocarditis and/or pericarditis
- All AESIs that are treatment-related

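### MAAEs and AEs leading to withdrawal are primary safety endpoints without restriction, but the planned outputs count only unsolicited events, so qualifying eDiary-captured solicited reactions are missed

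*SAP*

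**What the plan says.** **Endpoint.** For Part A, SAP Section 3.1.1 lists "Frequency of any serious AEs (SAEs), medically attended AEs (MAAEs), AEs leading to withdrawal from study participation" among the primary endpoints. For Part B, SAP Section 3.2.1 has "Frequency of any SAEs, MAAEs, AEs leading to withdrawal from study participation, and AESIs from Day 1 to EoS". Protocol Tables 1 and 2 agree. None of these is limited to unsolicited events, and neither is the running text of protocol Section 8.5.3.

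**Classification.** The list after protocol Table 5 (Section 7.4.3) names solicited reactions that need extra recording. The first item is "Solicited local or systemic AR that results in a visit to a healthcare practitioner (HCP), to be recorded as an MAAE". The second covers a solicited reaction that takes the participant out of the study and labels it an AE leading to withdrawal. Both go on the solicited AR page of the eCRF.

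**What unsolicited means.** Protocol Section 7.4.1 says "An unsolicited AE is any AE reported by the participant that is not specified as a solicited AR in the protocol", or one that is specified there but starts outside the 7-day period. Section 7.3.1 adds that a reaction reported at a call or visit and not already in the eDiary is described as unsolicited and entered on the AE page.

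**Planned outputs.** The overall summary in SAP Section 6.3.1.1 has the row "Any unsolicited MAAEs", and its row for discontinuation from the study is also limited to unsolicited events. So are the corresponding listings. SAP Section 6.3.1.2 plans a table of "All unsolicited TEAEs that are medically-attended" and a similarly limited discontinuation table. Protocol Table 7 has "Any Unsolicited MAAE" and an unsolicited-only withdrawal row. SAP Section 6.3.2 presents solicited reactions by grade, age group, day, onset, duration and persistence. It has no category for medical attendance or withdrawal.

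**The concern.** The endpoint and the table meant to report it do not cover the same events. The protocol deliberately brings some solicited reactions into the MAAE and withdrawal categories, and the word unsolicited in the outputs takes them out again.

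The events affected matter to a vaccine safety profile. Protocol Section 7.4.3 treats every solicited reaction as causally related, so these MAAEs are vaccine-attributed by rule. A reader of the clinical study report would take the MAAE row as the primary endpoint result, when it is a lower bound on it. The count would also depend on how a reaction was first reported rather than on what happened.

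**Working it through.** The documents give no rate for medically attended solicited reactions and no figure that can be reproduced. The check is therefore a tracing exercise, followed by arithmetic for scale.

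**Tracing one event.** A participant has chills on Day 2 and visits urgent care.

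| How it is first captured | Status under the protocol | In the MAAE table? |
|---|---|---|
| Entered in the eDiary, onset in Days 1 to 7 | Solicited AR, and an MAAE (7.4.3); solicited AR eCRF page | No: the row is unsolicited-only |
| Not in the eDiary, first mentioned at the Day 8 call | Unsolicited (7.3.1); AE eCRF page | Yes |
| Same symptom, onset after the 7-day period | Unsolicited (7.4.1); AE eCRF page | Yes |

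Only the first route is affected. It is also the main one, because Section 7.3.1 makes the eDiary the sole permitted source document for solicited reactions. The same tracing applies to a reaction that leads to withdrawal.

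**Could another output supply the number?**

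- *Grade tables.* Grade 4 headache, fatigue, myalgia, arthralgia, chills and injection site pain are each defined by "Requires emergency room visit or hospitalization", so those reactions are visible by arm. Grade is not a substitute for attendance, however. Grade 4 fever is defined by temperature, Grade 3 headache can mean prescription analgesia, and a lower-grade reaction can still prompt an urgent-care visit.
- *Serious events.* The serious TEAE rows are not worded as unsolicited-only, although the overall table is introduced as a summary of unsolicited TEAEs. Protocol Section 7.4.2 ties hospitalization to at least one overnight stay, so an outpatient or emergency visit without one need not be serious.
- *Disposition.* SAP Section 6.2.1 tabulates premature discontinuation by reason and arm. This shows AE withdrawals but does not link them to a solicited reaction.

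None of these yields the frequency of any MAAE or any AE leading to withdrawal.

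**Scale.** Arm size is up to 70 (protocol Section 8.3). Each participant whose only MAAE is an uncounted reaction lowers the percentage by 1/70 = 1.43 points. An arm reported as 0/70 would become 1/70 = 1.43%, 2/70 = 2.86% or 3/70 = 4.29%.

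The rates p below are assumptions. Expected number per arm = 70p, and the chance of at least one in an arm = 1 − (1 − p)^70.

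| Assumed p | Expected per arm | Points | Chance of at least one |
|---|---|---|---|
| 0.5% | 0.35 | 0.5 | 30% |
| 1% | 0.7 | 1.0 | 51% |
| 2% | 1.4 | 2.0 | 76% |
| 5% | 3.5 | 5.0 | 97% |

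For the MAAE row these expected deficits are upper limits. The row counts each participant once, MAAEs are collected for a year, and confirmed COVID-19 cases are MAAEs. A participant with a second, unsolicited MAAE is already in the row.

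**The case against.** The strongest reply is that keeping solicited and unsolicited events apart is deliberate. The SAP follows protocol Table 7. Protocol Section 7.4.4 tells investigators to look for MAAEs among the unsolicited AEs. Solicited reactions have their own primary endpoint, with tables by arm, grade and day and exact confidence intervals, and separate reporting avoids showing one event twice. The study is descriptive and tests no hypothesis.

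Much of this stands. It rules out three stronger readings that a reader might infer:

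- *That the worst reactions disappear from the safety report.* They do not. They appear by grade and in the solicited reaction listing, and AE withdrawals appear by reason in disposition.
- *That every medically attended solicited reaction goes uncounted.* Those first reported verbally are counted as unsolicited.
- *That the SAP departs from the protocol.* The restriction is in protocol Table 7 as well, so the conflict also lies inside the protocol: Table 7 against the endpoints, Section 7.4.3 and the text of Section 8.5.3.

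What does not stand is that separate reporting settles the matter. The endpoint covers any MAAE, the protocol says these reactions are MAAEs, and no planned table adds the two streams. Counting participants once in a combined row creates no double count.

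**Conclusion.** The mismatch is real and limited. As written, eDiary-captured solicited reactions with onset in Days 1 to 7 that lead to a healthcare visit or to withdrawal enter no MAAE or AE-withdrawal count, so the plan under-reports part of a primary safety endpoint. It matters mainly for MAAEs, because withdrawals are at least visible in disposition.

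The size cannot be found from the documents. If 1% to 5% of participants had a medically attended solicited reaction, the expected MAAE deficit is at most 0.7 to 3.5 participants per arm (1.0 to 5.0 points), and less where those participants have another MAAE.

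A reader might also infer that the omission narrows the safety contrast between dose levels. That needs attended reactions to rise with dose. This is plausible, but the documents do not quantify it, and the grade tables would still show dose-related reactogenicity.

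**What to change.** In protocol Table 7 and SAP Section 6.3.1.1, keep the unsolicited rows and add rows for *any (solicited or unsolicited)* MAAE and *any (solicited or unsolicited)* AE leading to withdrawal, with a matching listing. Draw on the solicited AR page together with the AE page of the eCRF, and count each participant once.

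Before programming, confirm that the solicited AR page flags medical attendance and withdrawal. The protocol says which reactions go on that page, but it does not show that these fields exist.

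The cost is minor table work and slightly less favourable MAAE percentages. If the flags are missing, the events would have to be identified from the source documents, where the protocol already requires them to be entered.
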